4.2 Safety and other Variables

Safety and other measures are study device placement, safety, and tolerability.

1. Placement success

Device successfully deployed at first try rate is defined as the percentage of the number of subjects with successful deployment at first attempt among the total number of subjects with first attempt.

Device successfully deployed at second try rate is defined as the percentage of the number of subjects with successful deployment at second attempt among the total number of subjects with second attempt.

Device successfully deployed rate is defined as the percentage of the number of subjects with successful deployment in either first or second attempt among the total number of subjects enrolled.

2. Ease of placement

Five categories of how easy the device placement have been collected: Very easy, Easy, Neither Easy nor Hard, Hard and Very Hard.

Five categories of device placement pain as rated by the subject: No Pain, Some Pain, Painful, Moderately Painful and Very Painful.

Question of insertions requiring mechanical cervical dilatation has been collected.

3. Adverse events

All Adverse Events (AEs) will be coded from verbatim text to PTs and grouped by system organ class (SOC) using the Medical Dictionary for Regulatory Activities (MedDRA) (version 17.0). AEs will be collected from the beginning of the study device placement procedure through to study exit. Pre-existing conditions that worsen during a study are to be reported as AEs.

Throughout the study, all AEs will be evaluated by the investigator and noted in the AE section of the CRF.

AEs will be classified as not related, unlikely related, probably related, or related events when considering their relationship to study device, study device placement/removal procedure. Also, AEs will be classified as mild, moderate, severe when considering their severity. If the severity or relationship of an AE is missing, the severity/relationship will be coded as severe, related, respectively, i.e. worst case scenario.

Treatment-emergent AEs (TEAEs): AEs that develop or that worsen in intensity during or after the exposure to the study device.

See Appendix 1 for handling of partial dates for AEs. If it cannot be determined whether the AE is treatment emergent due to a partial onset date then it will be counted as such.

Other AE variables include study device related AEs, AEs leading to study withdrawal, AEs leading to deaths, life threatening AEs, and serious AEs (SAEs).

4. Bleeding and spotting

The total number of bleeding or spotting days for each subject at each cycle will be counted. The total number of bleeding and spotting days for each subject at each cycle will also be counted separately.

5. Discontinuation rate and reasons for discontinuation

Removal rates

The removal rate is defined as the percentage of the number of subjects with device removed among the total number of subjects enrolled in the study by that time-point.

Expulsion rates

The expulsion rate is defined as the percentage of the number of subjects with device expulsion among the total number of subjects enrolled in the study by that time-point.

Discontinuation rate

The discontinuation rate is defined as the percentage of the number of subjects discontinued study among the total number of subjects enrolled in the study by that time-point.

Reasons for discontinuation

The following reasons have been collected for exiting study:

- Adverse Event;
- Withdrew Consent;
- Protocol Violation;
- Lost to Follow-up;
- Investigator/Sponsor Decision;
- Pregnancy;
- Screen Failure;
- Other.

5 Analysis Populations

Data analyses will be based on the analysis populations defined below. Analysis populations, including exclusions based on major protocol deviations (PDs), will be reviewed and approved by the Sebelia and its designee. Excluded cases will be documented together with the reason for exclusion.

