### **5. OBJECTIVES**

The scientific objective of this study is to evaluate the effectiveness, study device placement, safety, and tolerability of the LevoCept Intrauterine Contraceptive as birth control in parous and nulliparous women of child-bearing age.

The purpose of the study is to obtain the safety and effectiveness data necessary to support initiation of a longer-term Phase III Pivotal Clinical Study for LevoCept.

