## **12.2 Visit 2: LevoCept Placement (Day 1)**

See Section 4.1 for LevoCept insertion timing instructions. Subjects must have a negative urine pregnancy test just prior to LevoCept placement. Initiation of the LevoCept is consistent with standard IUD placement. Refer to the Clinician's Quick Use Guide and Investigator's Brochure for specific instructions.

If placement is unsuccessful, a second attempt may be made on the same day or within one (1) week following the first attempt. If a second attempt is also unsuccessful, the subject will be discontinued early from the study. The need for cervical dilation to facilitate placement of LevoCept will be left to the discretion of the investigator and subject; however, it is recommended that placement be tried first without prior cervical dilation. Use of cervical dilation will be recorded on the case report form. The need for pain control will also be left to the discretion of the investigator and subject. Any medications given for pain control will be recorded on the Concomitant Medications case report form.

Prior to LevoCept placement, the following evaluations will be completed:

- Entry criteria confirmed
- Vital signs and weight
- Pelvic Exam
- Pregnancy test, urine
- Prior and concurrent medications
- Any adverse events.

Following LevoCept placement, the following will be performed:

- LevoCept placement ease
- LevoCept placement pain
- LevoCept position (evaluated by Transvaginal Ultrasound)
- Concomitant contraception
- Need for contraception if LevoCept was not properly placed (If a subject believes the study device may have been expelled or is no longer in place, the subject should call for an urgent study visit and refrain from having sex or use appropriate non-hormonal contraception until further evaluation is completed. (See Section 4.7 for details)

- Review the completed practice diaries and discuss with the subject any further training that is required and answer any questions the subject may have about how to correctly complete the diaries.
- Instruct the subject to contact the site immediately if she thinks she has become pregnant.

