Note: The denominator for the percentages is the number of subjects (N) in the safety population.

Note: AEs are coded using MedDRA v xxx.

Note: Preferred terms are listed in descending order based on the overall subjects column.

Note: At each level of summation (overall, time frame, preferred term), subjects reporting more than one AE are counted only once.

AE=adverse event; MedDRA = Medical Dictionary for Regulatory Activities; TEAE = Treatment-Emergent Adverse Event.

Reference: Listing xxx.

Program Location: \\xx\xxx\xxx\xxx\xxxxxx\xxxxxxxxxxxxxxxx\xxxx\xxxxx.sas

date

time

Table 14.3.2.1
Deaths (All Enrolled Subjects)

Subject ID	Date of Death	Cause of Death	Primary Adverse Event # ^[1]	Comment
xxx-xxx	YYYY-MM-DD	SAE	xx	xxxxx
xxx-xxx	YYYY-MM-DD	Unknown		xxx
xxx-xxx	YYYY-MM-DD	Other, specify		xxx

[1] If subject's death was due to a SAE, provide primary Adverse Event.

Program Location: \\xx\xxx\xxx\xxx\xxxxxx\xxxxxxxxxxxxxxxx\xxxx\xxxxx.sas date time

Sebela Pharmaceuticals Development LLC
CMDOC-0022

Page x of y

Table 14.3.2.2
Serious Adverse Events (All Enrolled Subjects)

Programmer notes
This listing will follow a similar format as Listing 16.2.7.1

Table 14.3.2.3
Adverse Events as Primary Reason for Exiting Study (All Enrolled Subjects)

Programmer notes:
The following listings will follow a similar format as Listing 16.2.7.1:

CONFIDENTIAL

Sebela Pharmaceuticals Development LLC
CMDOC-0022

Page x of y

Table 14.3.5.1
Treatment Exposure (All Enrolled Subjects)

	All Subjects (N=xx)
Device Deployed at First Attempt	
Yes	n (%)
No	n (%)
If No, Made a Second Attempt	
n	n
Yes	n (%)
No	n (%)
Device Deployed at Second Attempt	
n	n
Yes	n (%)
No	n (%)
Device Deployed in either Attempt	
Yes	n (%)
No	n (%)
Number of Cycles with Device Use	
n	xx
Mean	xx.x
SD	xx.xx
Median	xx.x
Min	xx
Max	xx

Note: Percentages are based on the number of subjects specified in the column header, i.e. N, unless small n is specified for each category.

Reference: Listing xxx.

Program Location: \\xx\xxx\xxx\xxx\xxxxxx\xxxxxxxxxxxxxxxx\xxxx\xxxxx.sas

date

time

CONFIDENTIAL

Sebela Pharmaceuticals Development LLC
CMDOC-0022

Page x of y

Table 14.3.5.2
Device Placement and Subject Pain During the Procedure (All Enrolled Subjects)

	All Subjects (N=xx) n (%)
Difficulties with the Device Deployment	
n	n
Yes	n (%)
No	n (%)
Ease of Device Placement	
n	n
Very easy	n (%)
Easy	n (%)
Neither easy nor hard	n (%)
Hard	n (%)
Very hard	n (%)
Device Placement Pain	
n	n
No Pain	n (%)

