Reference: Listing xxx.

Program Location: \\xx\xxx\xxx\xxx\xxxxxx\xxxxxxxxxxxxxxxxxxxx\xxxx\xxxxx.sas

date

time

Table 14.3.5.4
Transvaginal Ultrasound (Safety Population)

	All Subjects (N=xx)
Device in Place	
n	n (%)
Yes	n (%)
No	n (%)

Reference: Listing xxx.

Program Location: \\xx\xxx\xxx\xxx\xxxxxx\xxxxxxxxxxxxxxxx\xxxx\xxxxx.sas date time

CONFIDENTIAL

Sebela Pharmaceuticals Development LLC
CMDOC-0022

Page x of y

Table 14.3.6.1.1
Bleeding and Spotting by Cycle (Safety Population)

Number of Days With	Cycle Statistic	All Subjects (N=xx)
Bleeding or Spotting	Cycle 1	
	n	xx
	Mean	xx.x
	SD	xx.xx
	Median	xx.x
	Min	xx
	Max	xx
	xxxxx	
	n	xx
	Mean	xx.x
	SD	xx.xx
	Median	xx.x
	Min	xx
	Max	xx
None		
Spotting		
Light Bleeding		
Medium Bleeding		
Heavy Bleeding		
Bleeding		
Heavier Flow than when not Using Hormones		
Heavier Flow than when not Using Hormones when Bleeding occurred		

CONFIDENTIAL

Note: Bleeding include Light Bleeding, Medium Bleeding and Heavy Bleeding.

Note: Menses question has the following choices: None, Spotting (minimal bleeding, no sanitary products required), Light Bleeding (pad, liner, or tampon used), Medium Bleeding (pad, liner, or tampon used), Heavy Bleeding (pad, liner, or tampon used).

Note: The heavy flow question is only asked when the subject responds with Spotting, Light Bleeding, Medium Bleeding, or Heavy Bleeding to the menses question.

Reference: Listing xxx.

Program Location: \\xx\xxx\xxx\xxx\xxxxxx\xxxxxxxxxxxxxxxxxxxx\xxxx\xxxxx.sas

date

time

Programmer note:

1. Table will continue with all cycles and remaining symptom.

2. Follow a similar format as Table 16.3.6.1.1 for:

Table 16.3.6.1.2 Bleeding and Spotting by Cycle (ECYC Population)

CONFIDENTIAL

Sebela Pharmaceuticals Development LLC
CMDOC-0022

Page x of y

Table 14.3.6.2.1
Occurrence and Severity of Dyspareunia in Number of Days by Cycle (Safety Population)

Cycle Statistic	All Subjects (N=xx)					
	No Pain	Some Pain	Painful	Moderately Painful	Very Painful	Not Applicable
Cycle 1						
n	xx	xx	xx	xx	xx	xx
Mean	xx.x	xx.x	xx.x	xx.x	xx.x	xx.x
SD	xx.xx	xx.xx	xx.xx	xx.xx	xx.xx	xx.xx
Median	xx.x	xx.x	xx.x	xx.x	xx.x	xx.x
Min	xx	xx	xx	xx	xx	xx
Max	xx	xx	xx	xx	xx	xx
xxxxx						
n	xx	xx	xx	xx	xx	xx
Mean	xx.x	xx.x	xx.x	xx.x	xx.x	xx.x
SD	xx.xx	xx.xx	xx.xx	xx.xx	xx.xx	xx.xx
Median	xx.x	xx.x	xx.x	xx.x	xx.x	xx.x
Min	xx	xx	xx	xx	xx	xx
Max	xx	xx	xx	xx	xx	xx

Reference: Listing xxx.

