3. Use XMED dataset.

CONFIDENTIAL

Sebela Pharmaceuticals Development LLC
CMDOC-0022

Page x of y

Listing 16.2.5.1
Device Placement (All Enrolled Subjects)
Part 1 of 2

First Attempt						Second Attempt				
Subject ID	Placement Performed	Device Lot Number	Date	Day of Current Menstrual Cycle[1]	Deployed	Device Lot Number	Attempt	Date	Day of Current Menstrual Cycle[1]	Deployed
xxx-xxx	Yes	xxx	YYYY-MM-DD	1	No, Explain		No	YYYY-MM-DD	1	No, Explain
xxx-xxx	Yes	xxx	YYYY-MM-DD	2	No	xxx	Yes	YYYY-MM-DD	2	No, Explain
xxx-xxx	Yes	xxx	YYYY-MM-DD	8	No	xxx	Yes	YYYY-MM-DD	8	Yes
xxx-xxx	Yes	xxx	YYYY-MM-DD	12	Yes			YYYY-MM-DD	12	Yes

[1] If subject has not been menstruating regularly due to hormonal contraception use or a recent pregnancy, day of current menstrual cycle is record as 00.

Program Location: \\xx\xxx\xxx\xxx\xxxxxx\xxxxxxxxxxxxxxxx\xxxx\xxxxx.sas date time

CONFIDENTIAL

Sebela Pharmaceuticals Development LLC
CMDOC-0022

Page x of y

Listing 16.2.5.1
Device Placement (All Enrolled Subjects)
Part 2 of 2

Subject ID	Difficulties with the Device Deployment	How easy was the device placement	Device Placement Pain	Medication given during the procedure	Mechanical Dilatation	Transvaginal Ultrasound		
						TVUS Performed	Date	Device in Place
xxx-xxx	No	Very easy	No Pain	Yes	Yes			
xxx-xxx	No	Easy	Some Pain	No	No	Yes	YYYY-MM-DD	No, Explain
xxx-xxx	Yes, Explain	Very hard	Very Painful	Yes	Yes	Yes	YYYY-MM-DD	Yes
xxx-xxx	Yes, Explain	Neither easy nor hard	Moderately Painful	Yes	Yes	Yes	YYYY-MM-DD	Yes

[1] If subject has not been menstruating regularly due to hormonal contraception use or a recent pregnancy, day of current menstrual cycle is recored as 00.

Program Location: \\xx\xxx\xxx\xxx\xxxxxx\xxxxxxxxxxxxxxxx\xxxx\xxxxx.sas

date

time

CONFIDENTIAL

Sebela Pharmaceuticals Development LLC
CMDOC-0022

Page x of y

Listing 16.2.5.2
Device Removal (All Enrolled Subjects)

Subject ID	Visit	Device Expel Prior to this visit/ Status	Date of Expulsion	Date of Procedure	Without Difficulty[1]	If No, Explain	Medication given during the procedure	Ease of Device Removal	Device Removal Pain
xxx-xxx	WEEK 52 - FOLLOW UP	Yes/ Complete	YYYY-MM-DD	YYYY-MM-DD			Yes	Very easy	No Pain
xxx-xxx	WEEK 52 - FOLLOW UP	Yes/ Partial	YYYY-MM-DD	YYYY-MM-DD	No	Required significant force to pull out with strings	No	Easy	Some Pain
xxx-xxx	WEEK 52 - FOLLOW UP	No		YYYY-MM-DD	No	Required use of IUD hook/ Other, Specify	Yes	Very hard	Very Painful

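### Placement success is measured by deployment alone, without the required Day 1 ultrasound, and no placement, expulsion or removal table is split by parity

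*SAP*

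**What the plan says.** **Success measure.** SAP 4.2 gives three placement rates: success at the first try, at the second try, and at either. The overall one reads "Device successfully deployed rate is defined as the percentage of the number of subjects with successful deployment in either first or second attempt", with all enrolled subjects as denominator. None of the three refers to device position. Table 14.3.5.1 reports the result in the row "Device Deployed in either Attempt", in a single All Subjects column.

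**Position check.** Protocol 12.2 lists among the steps after placement "LevoCept position (evaluated by Transvaginal Ultrasound", and then "Need for contraception if LevoCept was not properly placed". In the protocol's schedule of assessments (Table 1) the Visit 2 scan is marked without a condition. The scans at Visits 3 to 5 carry the if-indicated footnote, and scans are scheduled again at Week 52 and at exit. SAP Listing 16.2.5.1 holds Deployed in Part 1 and, separately in Part 2, "TVUS Performed" with its date and a Device in Place result.

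**Second attempt.** Protocol 12.2 states: "If placement is unsuccessful, a second attempt may be made on the same day or within one (1) week following the first attempt". Neither document defines an unsuccessful placement or a successful deployment.

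**Ultrasound summary.** Table 14.3.5.4, titled "Transvaginal Ultrasound (Safety Population", is one Yes/No block for Device in Place. It has no visit rows and no link to deployment.

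**Parity.** The objective in protocol section 5, repeated in SAP section 2, covers effectiveness, device placement, safety and "tolerability of the LevoCept Intrauterine Contraceptive as birth control in parous and nulliparous women of child-bearing age". The SAP tabulates parity at baseline (Table 14.1.6) and uses it to split the Pearl Index (Table 14.2.1) and pregnancy rate (Table 14.2.2). Tables 14.3.5.1 to 14.3.5.3, which cover deployment, ease, pain, dilation, expulsion and removal, have only an All Subjects column.

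**The concern.** Placement success is a named outcome, and the study is meant to support a Phase III decision. The protocol measures position on the day of placement, yet the success rate would be the same whatever that scan showed. A reader of the results would see a deployment rate and, in another table, a Device in Place percentage from an unspecified scan. Device in place on Day 1 could not be told apart from displacement found at Week 52 or exit.

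The parity split falls where it can say least. Pregnancies are expected to be very few, whereas every enrolled woman contributes placement data and every woman with a device contributes expulsion or removal data. A pooled placement rate can hide a difference between parous and nulliparous women, the two groups the objective names.

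**Working it through.** The documents state no target, expected rate or precision for placement, so there is no planned figure to reproduce. The check is a reading of the definitions against the shells, followed by arithmetic on assumed counts.

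**Step 1. Classify the four possible records under SAP 4.2.**

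| Deployed | Device in Place, Visit 2 scan | SAP 4.2 result | Deployed and in place |
|---|---|---|---|
| Yes | Yes | Success | Success |
| Yes | No | Success | Not a success |
| Yes | Scan missing | Success | Undetermined |
| No (both attempts, or no second) | Not applicable | Failure | Failure |

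The two measures differ only in rows 2 and 3.

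**Step 2. Size per woman.** Planned enrolment is about 250 (SAP 3.1). One woman in row 2 moves the rate by 1/250 = 0.4 percentage points. An assumed range of 0 to 10 such women gives 0 to 10/250 = 4.0 points.

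**Step 3. Illustration.** Assume 5 failed deployments in 250 and no missing scans. The SAP rate is 245/250 = 98.0% (exact 95% CI 95.4 to 99.3) whatever the scans show. The joint measure would be:

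| Deployed but not in place (assumed) | Deployed and in place | Exact 95% CI |
|---|---|---|
| 0 | 245/250 = 98.0% | 95.4 to 99.3 |
| 2 | 243/250 = 97.2% | 94.3 to 98.9 |
| 5 | 240/250 = 96.0% | 92.8 to 98.1 |
| 10 | 235/250 = 94.0% | 90.3 to 96.6 |

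**Step 4. What pooling over parity can hide.** Assume a pooled rate of 240/250 = 96.0% and the extreme case that all 10 failures are in nulliparous women. Neither document gives a parity mix, so a range is shown.

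| Nulliparous share (assumed) | Nulliparous rate | Parous rate |
|---|---|---|
| 30% (n = 75) | 65/75 = 86.7% | 100% |
| 50% (n = 125) | 115/125 = 92.0% | 100% |
| 70% (n = 175) | 165/175 = 94.3% | 100% |

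The planned table would show 96.0% in all three cases.

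**Step 5. Precision of a parity comparison.** Assume 125 women per group and success of 97% and 92%. The 95% half-width for the difference is 1.96 × √(0.97 × 0.03/125 + 0.92 × 0.08/125) = 0.056, or 5.6 points. A 5-point difference would have an interval of about -0.6 to 10.6 points. The columns would describe the groups; they would not settle a difference of that size.

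**Step 6. Precision where parity is split now.** The sample size text (SAP 3.2) assumes 1 pregnancy at 12 months, which is 0.5 per parity group if divided evenly.

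**The case against.** Much of the case on the other side stands, and it limits what can be claimed.

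- **Deployment is not the whole placement evaluation.** A reader might infer that the placement objective is answered by deployment alone. It is not: ease, pain, medication and dilation are summarised (SAP 6.2.9.3, Table 14.3.5.2), ultrasound has its own table, and Listings 16.2.5.1 and 16.2.5.3 show scans for each woman. The gap is in the success rate and in the missing Day 1 summary; listings do not yield a rate.
- **Bias is not shown.** A reader might infer that the reported rate must be too high. Because successful deployment is undefined, a site could record a device seen out of place as not deployed and make a second attempt, and row 2 of the table above would then be empty. The documents contain no form-completion rules that would settle this.
- **The parity question is not wholly unanswered.** Effectiveness is in the same objective sentence and is split by parity. The wording can also be read as describing the population, and protocol 20.7 asks only that placement ease and success be summarised.
- **Excluding out-of-place devices from the populations would be wrong.** A woman carrying a deployed device is exposed and belongs in the Safety population. SAP 5.3 and 5.5 build the Safety and EP populations on successful placement, and SAP 4.1 starts at-risk cycles there. Redefining success without separating those uses could remove exposed women from the adverse event tables and their pregnancies from the Pearl Index, in favour of the device.
- **The counts are assumed.** None of the illustrative failure counts, rates or parity mixes comes from the documents.

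**Conclusion.** The point holds in a limited form. The SAP's placement success rate does not use the Day 1 scan that the protocol requires, and as written it counts a record of Deployed = Yes with Device in Place = No as a success. Whether any such record exists depends on site practice with an undefined field. The size is therefore 0.4 points per woman, on the planned 250, with no basis in the documents for a total. Table 14.3.5.4 does not fill the gap, because it mixes the Day 1 scan with those at Week 52 or exit.

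The absence of parity columns is a weaker point but a fair one. The objective names the groups, parity is already collected, and the one outcome split by it is expected to have about 1 pregnancy at 12 months. With about 125 women per group (an assumption), the comparison would be imprecise, at roughly ±5.6 points, so it supports description only. Neither part affects the validity of the primary analysis. Both change what can be concluded about placement.

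**What to change.** 1. In SAP 4.2 and Table 14.3.5.1, keep the deployment rates and add a line for deployed and in place on the Visit 2 ultrasound, with all enrolled as denominator. Cross-tabulate it with deployment and show missing scans as their own category.
2. State in SAP 4.1, 5.3 and 5.5 that the start of at-risk cycles and the Safety and EP populations remain based on deployment. The added line then drops no exposed woman and no pregnancy.
3. Present Table 14.3.5.4 by analysis visit. SAP Table 1 already makes Day 1 its own window, so the Visit 2 scan separates without a new rule.
4. Add descriptive Parous / Nulliparous / All columns with 95% confidence intervals to Tables 14.3.5.1 to 14.3.5.3, using the column layout of Table 14.2.2. No test is needed.

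**Cost.** A few sentences of SAP text and some changes to table shells; all fields are already collected. The price is somewhat more tabulation, a success figure on the added line that may be lower than the deployment rate, and wide intervals for the parity comparison, which the report should acknowledge.

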### 15.4 Serious Adverse Event and Adverse Event Severity

The Investigator will assess the severity of the AE using the following general guidelines:

- **Mild:** An AE that is usually transient, requiring no special treatment, and does not interfere with the subject’s daily activities.
- **Moderate:** An AE that introduces a low level of inconvenience or concern to the subject and may interfere with daily activities, but is usually ameliorated by simple therapeutic measures.
- **Severe:** An AE that interrupts a subject’s usual daily activity and typically requires systemic drug therapy or other treatment (a severe AE may not necessarily qualify as an SAE).
- **Life-threatening:** An AE that put the subject at immediate risk of death from the event as it occurred. This does not include an event that might have led to death if it had occurred with greater severity.
- **Fatal:** An AE that was the cause of the subject’s death

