6.2.9.1 Adverse Events

Number of AEs will be summarised by SOC and/or PT for the following categories of TEAEs: all AEs, SAEs, AEs related to study device, AEs related to study device placement/removal procedure, AEs leading to death, AEs leading to study device removal and AEs as primary reason for exiting study. Patients with more than one occurrence of the same SOC (PT) will be counted only once within the SOC (PT) categorisation.

AEs will also be summarised similarly by severity (i.e. mild, moderate, severe), relationship to study device (i.e. not related, unlikely related, probably related, related), relationship to placement/removal procedure (i.e. not related, unlikely related, probably related, related) and onset time frame (i.e. 0-3 months, >3-6 months, >6-12 months, >12 months). Should a subject experience more than one occurrence of the same SOC (PT), the subject's worst occurrence (worst intensity/most related causality) will be retained in the tabulation.

All AEs, including AEs that started prior to the study device placement, will be presented in data listings. In addition, separate listings of all SAEs, AEs related to study device, AEs related to study device placement/removal procedure, AEs leading to death, AEs leading to study device removal and AEs as primary reason for exiting study will be provided. In case of any AEs reported from study device insertion failure subjects, selected AE tables will be repeated for all enrolled subjects for all AEs.

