14.3.1.5 Treatment-Emergent Adverse Events Leading to Study Device Removal (Safety Population)

14.3.1.6 Treatment-Emergent Adverse Events as Primary Reason for Exiting Study (Safety Population)

14.3.1.7 Treatment-Emergent Adverse Events Leading to Death (Safety Population)

CONFIDENTIAL

Sebela Pharmaceuticals Development LLC
CMDOC-0022

Page x of y

Table 14.3.1.8
Treatment-Emergent Adverse Events by System Organ Class, Preferred Term and Severity (Safety Population)

System Organ Class / Preferred Term	Events (N=xx) n			Subjects (N=xx) n(%)		
	Mild	Moderate	Severe	Mild	Moderate	Severe
Number (%) of subjects with any AEs				n (%)	n (%)	n (%)
System Organ Class 1	n	n	n	n (%)	n (%)	n (%)
Preferred Term 1	n	n	n	n (%)	n (%)	n (%)
Preferred Term 2	n	n	n	n (%)	n (%)	n (%)
System Organ Class 2	n	n	n	n (%)	n (%)	n (%)
Preferred Term 1	n	n	n	n (%)	n (%)	n (%)
Preferred Term 2	n	n	n	n (%)	n (%)	n (%)

Note: Only treatment-emergent AEs are summarised in this table. An AE that started on or after the date/time of study device placement, or an AE with an unknown/not reported onset date/time is defined as a TEAE.

Note: The denominator for the percentages is the number of subjects (N) in the safety population.

Note: AEs are coded using MedDRA v xxx.

Note: System organ classes are listed in descending order based on the subjects column; within each system organ class, preferred terms are listed in descending order based on the subjects column.

Note: At each level of summation (overall, system organ class, preferred term), subjects reporting more than one AE are counted only once using the highest severity.

AE=adverse event; MedDRA = Medical Dictionary for Regulatory Activities; TEAE = Treatment-Emergent Adverse Event.

Reference: Listing xxx.

Program Location: \\xx\xxx\xxx\xxx\xxxxxx\xxxxxxxxxxxxxxxx\xxxx\xxxxx.sas

date

time

CONFIDENTIAL

Sebela Pharmaceuticals Development LLC
CMDOC-0022

Page x of y

Table 14.3.1.9
Treatment-Emergent Adverse Events by System Organ Class, Preferred Term and Relatedness to Study Device (Safety Population)

System Organ Class / Preferred Term	Events (N=xx) n					Subjects (N=xx) n(%)				
	Not Related	Unlikely Related	Probably Related	Related	Not Applicable	Not Related	Unlikely Related	Probably Related	Related	Not Applicable
Number (%) of subjects with any AEs						n (%)	n (%)	n (%)	n (%)	n (%)
System Organ Class 1	n	n	n	n	n	n (%)	n (%)	n (%)	n (%)	n (%)
Preferred Term 1	n	n	n	n	n	n (%)	n (%)	n (%)	n (%)	n (%)

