Listing 16.2.7.1 Adverse Events (All Enrolled Subjects) Part 1 of 2

Subject ID	Any AE	AE #	System Organ Class // Preferred Term // Verbatim Text	Start Date(Study Day)/ End Date (Study Day)/ Duration/ TEAE	Severity	Worsening of Pre-existing Condition	Related to Bleeding	Relationship to Study Device	Relationship to Placement/ Removal Procedure	Action Taken with Study Device	Treatment of Event	Outcome
xxx-xxx	No											
xxx-xxx	Yes	1	xxxxx// xxxxx// xxxxx	YYYY-MM-DD (xx)/ YYYY-MM-DD (xx)/ xx/ No	Mild	No	No	Not Related	Not Related	None	Medication	Recovered
		2	xxxxx// xxxxx// xxxxx	YYYY-MM-DD (xx)/ YYYY-MM-DD (xx)/ xx/ Yes	Moderate	Yes	Yes	Unlikely Related	Unlikely Related	Removed	Non-Drug Treatment	Resolved with Sequelae
		3	xxxxx// xxxxx// xxxxx	YYYY-MM-DD (xx)/ YYYY-MM-DD (xx)/ xx/ Yes	Life Threatening	No	No	Probably Related	Probably Related	Expelled	Hospitalization	Ongoing
		4	xxxxx// xxxxx// xxxxx	YYYY-MM-DD (xx)/ YYYY-MM-DD (xx)/ xx/ Yes	Fatal	Yes	Yes	Related	Related	Not Applicable	None	Fatal
xxx-xxx	Yes	1	xxxxx// xxxxx// xxxxx	YYYY-MM-DD (xx)/ YYYY-MM-DD (xx)/ xx/ Yes	Moderate	No	No	Not Applicable	Not Applicable	Expelled	Hospitalization	Unknown

[1] Did the AE require inpatient hospitalization or prolong an existing hospitalization?

[2] Did the AE result in persistent or significant incapacity or substantial disruption of the ability to conduct normal life functions?

[3] Did the AE result in a congenital anomaly or birth defect?

Note: An AE that started on or after the date/time of study device placement, or an AE with an unknown/not reported onset date/time is defined as a TEAE.

Note: AEs are coded using MedDRA v xxx.

Note: Study day is relative to the date of study device successfully deployed. Duration in days is calculated as end date –start date +1.

AE = Adverse Event; MedDRA = Medical Dictionary for Drug Activities; TEAE = Treatment-Emergent Adverse Event.

Program Location: \\x\xxx\xxx\xxx\xxxxxx\xxxxxxxxxxxxxx\xxx\xxxx.sas

date

time

Programmer notes: Sort by AE # within each subject.

CONFIDENTIAL

Sebela Pharmaceuticals Development LLC
CMDOC-0022

Page x of y

Listing 16.2.7.1
Adverse Events (All Enrolled Subjects)
Part 2 of 2

Subject ID	Any AE	AE #	Serious	Result in Death	Date of Death/ Death Certificate/ Autopsy	Life-threatening	Hospitalization[1]/ Date of Admission/ Date of Discharge	Life functions[2]	Birth Defect[3]	Important Medical Event	Intervention
xxx-xxx	No										
xxx-xxx	Yes	1	No	No		No		No		No	No

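### The SAP's severity tables have three grades where the protocol and the SAP's own listing have five, and no rule says where life-threatening and fatal events go

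*SAP*

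**What the plan says.** Protocol 15.4 sets the scale: "The Investigator will assess the severity of the AE using the following general guidelines". Five grades follow. Above mild, moderate and severe stands life-threatening, defined as "An AE that put the subject at immediate risk of death from the event as it occurred", and then fatal, "An AE that was the cause of the" subject's death. Protocol 20.7 promises adverse-event summaries by severity.

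The SAP uses a shorter scale. Section 4.2 says "AEs will be classified as mild, moderate, severe when considering their severity", and section 6.2.9.1 repeats it for the analysis: "AEs will also be summarised similarly by severity (i.e. mild, moderate, severe"). The shells for Tables 14.3.1.2.1 and 14.3.1.8 have these three severity columns only, and Table 14.3.1.2.2 is to follow the layout of 14.3.1.2.1. A footnote to Table 14.3.1.8 says that "subjects reporting more than one AE are counted only once using the highest severity".

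The SAP's listing of the same data is different. In Listing 16.2.7.1 the severity column shows "Life Threatening" and also Fatal among its example values.

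On missing grades, SAP 4.2 says: "If the severity or relationship of an AE is missing, the severity/relationship will be coded as severe, related, respectively, i.e. worst case scenario".

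**The concern.** The protocol collects five grades and the SAP expects to list five, but its severity tables have room for three. The two grades without a column are the two most serious. A programmer who meets a life-threatening or fatal value has no instruction and must choose between leaving the event out and recoding it. Neither choice would be visible to someone reading the table.

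The study is meant to support starting a Phase III trial, and summaries by severity are part of the safety reporting that the protocol promises. A reader should be able to see from them how many events lay above severe, and the event counts should agree with the other adverse-event tables.

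**Working it through.** No planned figure or sample-size calculation bears on this point. The check compares the sets of categories.

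| Place | Severity grades provided |
|---|---|
| Protocol 15.4 | Mild, moderate, severe, life-threatening, fatal (5) |
| SAP Listing 16.2.7.1, severity column | Values include life-threatening and fatal |
| SAP 4.2 and 6.2.9.1 | Mild, moderate, severe (3) |
| Tables 14.3.1.2.1 and 14.3.1.2.2 | Mild, moderate, severe, plus a total (3) |
| Table 14.3.1.8 | Mild, moderate, severe, for events and for subjects (3) |

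Grades without a severity column: 5 − 3 = 2. Stated rules that map five grades to three: none. SAP 8.2 lists two departures from the protocol, one on the safety population and one on pre-treatment pregnancies in the EP population. The shorter scale is not among them.

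**Effect on event counts.** Let the numbers of mild, moderate, severe, life-threatening and fatal events be a, b, c, d and e, so that all events number a + b + c + d + e.

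- If the upper two grades are left out, the three columns of Table 14.3.1.2.1 sum to a + b + c. They fall short of all events by d + e. Either the columns do not add up to the total, or the total does not add up to the table's own denominator, which is the number of events. Table 14.3.1.8 would fall short of Table 14.3.1.3.1 by the same amount.
- If they are merged, the Severe column holds c + d + e. The sums agree, but the reader cannot separate d and e from c and is not told that they are there.

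**Effect on subject counts.** Table 14.3.1.8 counts each woman once, at her highest grade. If that grade is life-threatening or fatal, the shell has no column for it. Leaving her out fails the footnote. Counting her as severe satisfies it only under a merging rule that the SAP does not state.

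**Other SAP conventions.**

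- SAP 10.2 requires categorical summaries to show every planned category that a subject could have reported. The three-column shells conflict with that.
- The relatedness part of these shells includes a Not Applicable category that the SAP text does not name but Listing 16.2.7.1 does. The severity columns were not aligned with the listing in the same way, which suggests an oversight.
- Coding a missing grade as severe and calling it the worst case fits a three-level scale. On the protocol's scale, severe is the third of five.

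**Where these events do appear.**

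- Fatal events have Table 14.3.1.7, a row in Table 14.3.1.1.1, Table 14.3.2.1 and Listing 16.2.7.5.
- Life-threatening events meet a seriousness criterion in Protocol 15.1. They therefore enter Tables 14.3.1.4.1 and 14.3.1.4.2, and Table 14.3.2.2 lists them in the format of Listing 16.2.7.1, which has both a severity column and a separate life-threatening column.
- SAP 4.2 names life-threatening events as a variable of their own. The table index has no summary table for it, and Table 14.3.1.1.1 has no row for it.

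**The case against.** The strongest defence is that the SAP implies a three-level scale with severe at the top. Section 4.2 applies the three grades to all adverse events and treats severe as the worst case, so a life-threatening event would naturally be counted as severe. Nothing says that such events are discarded, and SAP 10.2 could even be read as requiring the extra categories to be shown. This stands to the extent that omission is only one of two possible outcomes. It does not remove the defect: the merging is nowhere stated, it departs from the protocol's scale without being recorded, and the shells and section 10.2 point in different directions.

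Three stronger readings are tempting, and the documents do not support them.

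- A reader might infer that the worst events disappear from the report and that harm is understated. They do not disappear. The death and serious-event displays carry them, and Protocol 15.1 makes any ectopic pregnancy serious whatever its severity grade.
- A reader might infer that a woman with a life-threatening event would be shown at a milder grade because of another event. That would breach both the worst-occurrence rule in SAP 6.2.9.1 and the footnote to Table 14.3.1.8, so it would be a programming error and not the plan.
- A reader might size the problem as a share of the 250 planned women. The denominators do not allow it. Table 14.3.1.2.1 uses events, and Table 14.3.1.8 uses the safety population, which the SAP limits to successful placements.

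**Conclusion.** The inconsistency is real and can be read directly from the text: two of the protocol's five severity grades have no cell in three planned tables, and no rule says how to handle them. It is a conflict between stated rules and not merely a missing detail, because the three-grade wording contradicts the protocol, the SAP's own listing and the convention in SAP 10.2.

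Its reach is limited. It affects the severity summaries and the unreported life-threatening variable, not the primary endpoint and not the death or serious-event tables. The number of affected events is expected to be small, and the documents give no basis for a figure. Whether events would be left out or merged depends on programming choices that the SAP leaves open. The conclusion that life-threatening events reach the serious-event tables assumes that sites apply Protocol 15.1 and 15.4 consistently. The point should be corrected before the tables are produced.

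**What to change.** Preferred: use the protocol's five grades in SAP 4.2 and 6.2.9.1, add Life-threatening and Fatal columns to Tables 14.3.1.2.1, 14.3.1.2.2 and 14.3.1.8, and take the highest severity over all five. Reword the missing-severity rule, since severe is not the worst grade on that scale.

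Minimum: state in SAP 4.2 that life-threatening and fatal events are counted as severe in the severity tables, footnote this in all three, record it in SAP 8.2 as a departure from the protocol, and add a life-threatening row to Table 14.3.1.1.1 so that the variable named in SAP 4.2 is reported.

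The preferred change costs two columns in three tables and a few sentences of text; the minimum costs less still. Neither needs new data.
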